#### 4.0 SUBJECT SCREENING AND REGISTRATION PROCEDURES

After informed consent is obtained and PRIOR to the initiation of protocol therapy all patients satisfying the inclusion/exclusion criteria must have eligibility confirmed by the Coordinating Center. The patient will not be considered registered and enrolled in the study until all information is confirmed by the Coordinating Center's Multi-Site Coordinator.

Patient registration for this trial will be centrally managed as described below:

A potential study subject who has been screened for the trial and who has signed the Informed Consent document will be initially documented by the participating site on a Screening and Enrollment Log.

It is the responsibility of the local site investigator to determine patient eligibility prior to submitting patient registration request to the Coordinating Center. After patient eligibility has been determined, a copy of the **completed** Eligibility Worksheet together with all the pertinent de-identified source documents will be submitted by the requesting site to the Coordinating Center, by email to [[contact]](mailto:[contact]).

A Multi-Site Coordinator of the Coordinating Center, who acts as the registrar, will review the submitted documents and process the registration. Sites should inform the Multi-Site Coordinator of a potential registration by 5 p.m. on the day prior to registration. Same day registrations cannot be guaranteed.

An email will be sent by the registrar to the requesting site registrar to confirm patient registration and to provide the study identification number that has been assigned to the patient. In addition, a copy of the Eligibility Worksheet signed and dated by the registrar, will be sent back to the requesting site registrar.

Patients found to be ineligible for participation after being consented will be considered screen failures, and documented as such in the Screening and Enrollment Log. These patients will not have study identification number assigned to them, and will not receive study treatment.

## 5.0 TREATMENT PLAN

### 5.1 Treatment Dosage and Administration

Protocol treatment must start within 14 business days of enrollment to the study. The interleukin-2 (Proleukin) and Nivolumab (Opdivo) will be stored and prepared as described in the approved labels.

- 5.1.1 Therapy will start with high dose interleukin-2 (HD IL2) on week1 (day 1-5) and again on week 3 (day 1-5). Nivolumab will start on week 2 (optimally day 1 but can be given up to 3 weeks after IL-2 start but NOT be on the same week as any HD IL2 cycle) and continue every 4 weeks for up to 48 weeks on study unless one of the dose delay or stopping rules apply.
- 5.1.2 HD IL-2 will be administered in standard fashion at a fixed dose of 600,000 IU/kg/dose every 8 hours for a total of up to 14 doses (considered as one cycle) over 5 consecutive days (D1-D5), followed by a 9-day break and then another cycle at the same dose over another 5 consecutive days (D15-D19). Each HD IL-2 course consists of two cycles of up to 14 doses each separated by 9 days of rest.

Monitoring, supportive care measures for HD IL2 will be per institutional guidelines. The standard current guidelines for HD IL-2 administration based on Schwartzenruber et al. have proven to be safe at the participating institutions in the study over the years and will be used for this protocol.

Pre-medications and concurrent medications: Per institutional guidelines at each site usually include anti-emetics, anti-histamines, antipyretics/anti-inflammatory agents, anti-motility/anti-diarrheal agents, proton pump inhibitors, vasopressors as needed, medications for rigors as needed, hydration including boluses and maintenance fluids. It is recommended but not mandated that subjects be given anti-emetics for as needed (prn) use after each IL-2 therapy week to treat residual nausea. Furosemide (a loop diuretic) may also be given per treating investigator's discretion following each IL2 week. Please see IL-2 guidance document for more details.

Subjects will undergo placement of a central venous catheter before each course or cycle of therapy per institutional preferences.

NOTE: If the treating investigator determines another course of HD IL-2 beyond the 2 cycles after week 12 of protocol therapy specified in the protocol are in the

subject's best interests, it is permissible and will be recorded in follow-up. If so, nivolumab should be held during IL2 weeks. No protocol specified assessments are required for the repeat course.

- 5.1.3 Nivolumab will be administered intravenously at a standard dose of 480 mg/dose every 4 weeks starting on week 2 (ideally day 1 of week 2 but can be given up to 3 weeks after IL-2 start but NOT be on the same week as any HD IL2 cycle) and continued as long as clinical benefit continues as determined by the treating investigator for up to 48 weeks on study.
- 5.1.4. The first 3 patients will be treated with sequential (rather than interspersed) treatment. They will receive 2 cycles of HD-IL2 given in standard fashion (two 5-day cycles one week apart) followed by nivolumab starting the week after the second IL-2 cycle and continuing every 4 weeks as per standard nivolumab dosing.

We will perform a safety analysis after the first 3 patients are treated and if 2/3 patients suffer a grade 3 or 4 immune related toxicity, the study will stop. The 4th patient will not be enrolled until after the analysis of the 3 patient cohort is complete and submitted to the regulatory bodies

**REGIMEN DESCRIPTION**

Agent	Premedications	Dose	Route	Schedule
Interleukin-2	Per institutional guidelines, none mandated.	600,000 IU/kg/dose Ω every 8 hours Prepare and store according to approved label.	IV over 15 minutes (± 5 minutes)	Week 1 (Days 1-5) AND Week 3 (Days 1-5)
Nivolumab	Per institutional guidelines, none mandated.	480 mg/dose Prepare and store according to approved label.	IV over 60 (± 10 minutes) minutes	Every 28 days starting Week 2 (Optimally Day 1 but can be given up to 3 weeks after IL-2 start)

ΩThe IL-2 dose should be calculated separately on D1 and D15.

**NOTE:** Infusions may be performed ±3 business days for reasons such as observed holidays, inclement weather, scheduling conflicts, etc. It should be clearly documented in subject's chart and case report forms.

- 5.1.5 Missed doses  
Missed doses of HD IL-2 are not made up. Missed doses of Nivolumab can be made up within 72 hours of scheduled time and skipped if outside of 72 hours

## 5.2 Toxicities and Dosing Delays/Dose Modifications

Any patient who receives treatment on this protocol will be evaluable for toxicity. Each patient will be assessed for the development of toxicity according to the Time and Events Table (Section 6.4). Toxicity will be assessed according to the NCI Common Terminology Criteria for Adverse Events (CTCAE), version 4.0. Dose adjustments should be made according to the system showing the greatest degree of toxicity.

**Dose modifications** in strength are not permitted for either IL2 or nivolumab.

### Dosing delays:

- **DURING IL-2 weeks**
  - Individual doses of IL-2 within each cycle may be skipped by the treating investigator at his or her discretion. Skipped doses will not be made up.
  
- **AFTER IL-2, BEFORE NIVOLUMAB**
  - All toxicities (with the exception of fatigue) attributed to IL-2 administration should have resolved or recovered to grade 1 or resolved or to baseline prior to starting nivolumab
  - Fatigue should have recovered to grade 2 or better
  - If toxicities have not improved to the levels listed above, nivolumab and the 2nd cycle of IL-2 should be held until toxicities improve to the above levels
  - If nivolumab or IL-2 is delayed >6 weeks as a result of a toxicity, the subject must be permanently discontinued from study therapy with the following exception:
    - If a steroid taper (to manage drug-related adverse events) is the reason for treatment delay of >6 weeks, and the subject's adverse events recover to grade 1 or better, continuation on study could be possible if approved by the principal investigator
  
- **AFTER NIVOLUMAB, PRIOR TO 2nd IL-2 CYCLE**
  - All immune mediated toxicities should have recovered to grade 1 or better prior to starting the second dose of IL-2 and subjects should be off systemic steroids or on a dose of ≤ prednisone 10mg (or equivalent alternative steroid).
  - Fatigue should have recovered to grade 2 or better
  - If specific toxicities are of unclear attribution (including for example: diarrhea, increased LFTs, cardiovascular disorders, mental status changes, pulmonary disorders and rash) they should be treated as possibly related to nivolumab and treated as per the tables in section 5.2.2. These toxicities must improve to grade 1 or better prior to proceeding with the second week of IL-2 therapy.
  - If toxicities have not improved to the levels listed above, nivolumab and the 2nd cycle of IL-2 should be held until toxicities improve to the above levels

- If nivolumab or IL-2 is delayed >6 weeks as a result of a toxicity, the subject must be permanently discontinued from study therapy with the following exception
  - If a steroid taper (to manage drug-related adverse events) is the reason for treatment delay >6 weeks, and the subject's adverse events recover to grade 1 or better, continuation on study could be possible if approved by the principal investigator
  
- **DURING NIVOLUMAB ONLY TIME PERIOD:**
  - With any grade 2 or higher **non-hematologic toxicity**, hold nivolumab and refer to section 5.2.1 Events of Interest for relevant management guidelines. If adverse event is not an event of interest and improves to grade 1 or better with symptomatic management and/or supportive medications, nivolumab may be resumed in ≥ 2 weeks. If non-hematologic toxicity does not improve to grade 1 or better within 6 weeks from prior dose, nivolumab should be discontinued.

**5.2.1 IMMUNE MEDIATED EVENTS OF INTEREST (ONCE AT LEAST 1 DOSE OF NIVOLUMAB HAS BEEN ADMINISTERED) - APPLY TO NIVOLUMAB ONLY:**

Certain adverse events that are possibly immune mediated warrant special monitoring and management, and are outlined below to guide investigators.

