**5.2.1.1 Pulmonary:**

Rule out non-inflammatory causes. If non-inflammatory cause, treat accordingly and continue protocol therapy. Evaluate with imaging and pulmonary consultation.

Grade of pneumonitis (NCI CTCAE v4)	Management	Follow-up
Grade 1 Radiographic Changes Only	
 
• Consider delay of nivolumab
 
• Monitor for symptoms every 2-3 days
 
• Consider pulmonary and infectious disease consultations
 
	
 
• Re-image at least every 3 weeks
 
• If worsening, treat as grade 2,3 or 4
 

Grade 2 Mild to moderate new symptoms	
 
• Delay nivolumab
 
• Consult pulmonary and infectious disease
 
• Monitor symptoms daily, consider hospitalization
 
• 1.0mg/kg/day methylprednisolone IV or oral equivalent
 
• Consider bronchoscopy and/or lung biopsy
 
	
 
• Re-image every 1-3 days
 
• Consider prophylactic antibiotics while on steroids
 
• If improves:                             
 
• When symptoms return to near baseline, taper steroids over at least one month
 
• Resume nivolumab and IL-2 if the event improves to grade 0 or 1 within 12 weeks and corticosteroids have been reduced to the equivalent of ≤ 10mg oral prednisone per day
 
 
 
• If not improving after 2 weeks or worsening, treat as grade 3 or 4
 

Grade 3 or 4 Severe new symptoms and/or new or worsening hypoxia
	
 
• Discontinue nivolumab.
 
• Hospitalize
 
• Consult pulmonary and infectious disease
 
• 1-2mg/kg/day methylprednisolone IV or IV equivalent
 
• Add prophylactic antibiotics for opportunistic infections like PCP
 
• Consider bronchoscopy and/or lung biopsy
 
	
 
• If improves to baseline:             
 
• Taper steroids for at least 6 weeks
 
 
 
• If not improving after 48 hours or worsening             
 
• Add additional immunosuppressive agent(s) (e.g. infliximab, cyclophosphamide, intravenous immunoglobulin or mycophenolate mofetil)
 
 
 

---	--	---

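### Before the second IL-2 cycle, 5.2 ends study therapy after a toxicity delay of more than 6 weeks, but eight 5.2.1 rows direct restart on improvement within 12 weeks; precedence is not stated

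*Combined protocol and SAP*

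**What the plan says.** Section 5.2 (Dosing delays) has a block for the period after nivolumab and before the second IL-2 cycle. If either drug is "delayed >6 weeks as a result of a toxicity, the subject must be permanently discontinued from study therapy with the following exception", and that exception is a delay caused by a steroid taper. Even then, the "adverse events recover to grade 1 or better, continuation on study could be possible if approved by the principal investigator". The same block requires immune-mediated toxicity to be at grade 1 or better, and prednisone at or below 10 mg, before the second cycle. For toxicities of unclear attribution it says "they should be treated as possibly related to nivolumab and treated as per the tables in section 5.2.2". There is no section 5.2.2; the tables are in 5.2.1.

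The 5.2.1 heading carries the qualifier "ONCE AT LEAST 1 DOSE OF NIVOLUMAB HAS BEEN ADMINISTERED) - APPLY TO NIVOLUMAB ONLY". Its lead-in says that such events "warrant special monitoring and management, and are outlined below to guide investigators". The grade 2 pneumonitis row then reads "Resume nivolumab and IL-2 if the event improves to grade 0 or 1 within 12 weeks", with the added condition that steroids are down to 10 mg prednisone or less. Seven other rows say the same in substance. None of the eight asks for approval.

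In 5.2.1.7, the renal grade 4 row tells the site to discontinue nivolumab in the management column and to resume nivolumab and IL-2 in the follow-up column.

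**The concern.** A patient whose immune-mediated event is slow to settle can fall under both texts. One says study therapy must end; the other says to restart both drugs. Re-exposure to high-dose IL-2 and a PD-1 inhibitor after such an event is a safety decision, and four sites could reasonably decide it differently. The biweekly cross-site calls in section 12.0 would help to align practice, but they are required only until phase Ib is completed.

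**Working it through.** No figure in the plan can be reproduced here, so the check is a row count, a comparison of the two texts, and dates from the schedule.

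**Rows with the 12-week restart text.** Pulmonary 1 of 3, gastrointestinal 2 of 4, endocrine 1 of 5, hepatic 0 of 3, neurological 0 of 4, skin 2 of 2, renal 2 of 3. Total: 1 + 2 + 1 + 0 + 0 + 2 + 2 = 8 of 24, in 5 of 7 tables. Symptomatic hyperthyroidism, hepatic grade 2 and neurological grade 2 also restart IL-2, without a 12-week term, so 8 + 3 = 11 of 24 rows restart IL-2.

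**The two texts compared.**

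| | 5.2, before IL-2 cycle 2 | Eight rows in 5.2.1 |
|---|---|---|
| Grade needed to restart | 1 or better | 0 or 1 |
| Steroid level | at or below 10 mg prednisone | same |
| Time limit | 6 weeks of delay | improvement within 12 weeks |
| Beyond 6 weeks | taper delays only | no restriction |
| Approval beyond 6 weeks | principal investigator | none named |

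**Where the instructions are opposite.** All eight rows name a taper of at least one month. For pneumonitis, for example: "When symptoms return to near baseline, taper steroids over at least one month". If the event settles early and the taper causes the long delay, the 5.2 exception can apply and the texts differ only on approval. If the event itself holds dosing beyond 6 weeks and reaches grade 1 within 12, 5.2 says stop and the row says restart.

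| Row | What happens to a slow event | Opposite instructions? |
|---|---|---|
| Diarrhea/colitis grade 2 | no time-based step to discontinuation | yes |
| Diarrhea/colitis grade 3 | no such step | yes |
| Adrenal insufficiency | no such step | yes |
| Rash grade 1-2 | no such step | grade 2 only; grade 1 already meets the restart level |
| Rash grade 3-4 | site may delay or discontinue | only if the site delayed |
| Pneumonitis grade 2 | "If not improving after 2 weeks or worsening, treat as grade 3 or 4", and nivolumab is then stopped | little room |
| Renal grade 2-3 | beyond 7 days, treated as grade 4 | leads to the row below |
| Renal grade 4 | discontinue and resume in one row | contradicts itself |

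**Dates.** Day 1 is the first IL-2 dose, on the interspersed schedule with nivolumab on day 8. I assume that the 6 weeks run from the scheduled dose, which the plan does not say.

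- IL-2 cycle 2 is due on day 15, so its limit is 15 + 42 = day 57.
- Nivolumab dose 2 is due on day 8 + 28 = 36, so its limit is 36 + 42 = day 78.
- A delay of either drug triggers the rule, so day 57 comes first.
- The start of the 12 weeks is not stated. Counted from an assumed onset on day 8 to day 14, it ends on 8 + 84 = day 92 to 14 + 84 = day 98.
- Gap after the day 57 limit: 92 - 57 = 35 days to 98 - 57 = 41 days.
- The DLT period ends on 8 + 28 = day 36, before either limit.

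The gap is an illustration. It does not bound the date of restart, because the rows put the 12 weeks on improvement and separately require steroid reduction.

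**The case against.** The best defence is that the texts fit together: 5.2 uses mandatory language, while the tables are described as guidance and headed as applying to nivolumab only. On that reading 5.2 acts first, and a patient stopped at 6 weeks never reaches the 12-week condition. This is a sensible reading and probably the intended one, but it is not written down. The 6-week rule covers a nivolumab delay as well as an IL-2 delay, so the nivolumab-only label does not separate the two texts. Eleven rows restart IL-2 despite that label, and 5.2 itself sends patients to the tables.

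Several limits on the point stand:

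- The window is short, from nivolumab on day 8 to cycle 2 on day 15 unless dosing is held. It does not arise for the first 3 patients, who are treated sequentially, or when nivolumab starts after cycle 2.
- Oversight in phase II does not rest on the calls alone. The Data and Safety Monitoring Committee and the site teams meet quarterly, and section 5.5 lets treatment stop for unacceptable adverse events.

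A reader might infer that the tables permit restart during active toxicity or on high-dose steroids. They do not, since the thresholds match those in 5.2. Nor do all eight rows conflict for every delay between 6 and 12 weeks: taper delays, pneumonitis escalation and the discontinue option for grade 3-4 rash remove much of that.

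**Conclusion.** The point holds in a limited form and should be corrected. Eight rows carry a restart clock that 5.2 does not allow before the second IL-2 cycle, and they omit the approval that 5.2 requires. Truly opposite instructions are confined to toxicity that itself delays dosing beyond 6 weeks, mainly grade 2 and 3 diarrhea/colitis, adrenal insufficiency and grade 2 rash, and grade 3-4 rash where the site chose delay. The renal grade 4 row is wrong as written whichever section governs, because its two instructions cannot both be followed.

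The row counts come directly from the tables. The day 57 limit assumes the planned schedule and counting from the scheduled dose; the 35 to 41 days also assume onset on day 8 to day 14 and counting from onset. The documents give no basis for a patient count. Sample size, DLT assessment and response evaluability are unaffected, so a reader should not infer a threat to the primary endpoints.

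**What to change.** 1. Add to 5.2.1: *Resumption under these tables is subject to the delay limits in 5.2 for the relevant treatment period. Before the second IL-2 cycle, resumption after a delay of more than 6 weeks is allowed only if the delay is due to a steroid taper, the event is grade 1 or better, and the principal investigator approves.*
2. Delete the resume instruction from the renal grade 4 row so that it reads discontinue.
3. Have the sponsor confirm how the separate 6-week wording for the nivolumab-only period, in the last block of the 5.2 dosing delays, applies to events of interest. The same tables are used there, so a fix limited to the earlier window could suggest that the tables override it.
4. As a clerical matter, change the reference to 5.2.2 to 5.2.1.

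The cost is a wording amendment. The first change keeps the protocol's own stricter rule. The downside is that a few patients with slow-resolving events lose the option to restart on study.

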**5.2.1.1 Pulmonary:**

Rule out non-inflammatory causes. If non-inflammatory cause, treat accordingly and continue protocol therapy. Evaluate with imaging and pulmonary consultation.

Grade of pneumonitis (NCI CTCAE v4)	Management	Follow-up
Grade 1 Radiographic Changes Only	
 
• Consider delay of nivolumab
 
• Monitor for symptoms every 2-3 days
 
• Consider pulmonary and infectious disease consultations
 
	
 
• Re-image at least every 3 weeks
 
• If worsening, treat as grade 2,3 or 4
 

Grade 2 Mild to moderate new symptoms	
 
• Delay nivolumab
 
• Consult pulmonary and infectious disease
 
• Monitor symptoms daily, consider hospitalization
 
• 1.0mg/kg/day methylprednisolone IV or oral equivalent
 
• Consider bronchoscopy and/or lung biopsy
 
	
 
• Re-image every 1-3 days
 
• Consider prophylactic antibiotics while on steroids
 
• If improves:                             
 
• When symptoms return to near baseline, taper steroids over at least one month
 
• Resume nivolumab and IL-2 if the event improves to grade 0 or 1 within 12 weeks and corticosteroids have been reduced to the equivalent of ≤ 10mg oral prednisone per day
 
 
 
• If not improving after 2 weeks or worsening, treat as grade 3 or 4
 

Grade 3 or 4 Severe new symptoms and/or new or worsening hypoxia
	
 
• Discontinue nivolumab.
 
• Hospitalize
 
• Consult pulmonary and infectious disease
 
• 1-2mg/kg/day methylprednisolone IV or IV equivalent
 
• Add prophylactic antibiotics for opportunistic infections like PCP
 
• Consider bronchoscopy and/or lung biopsy
 
	
 
• If improves to baseline:             
 
• Taper steroids for at least 6 weeks
 
 
 
• If not improving after 48 hours or worsening             
 
• Add additional immunosuppressive agent(s) (e.g. infliximab, cyclophosphamide, intravenous immunoglobulin or mycophenolate mofetil)
 
 
 

---	--	---

**5.2.1.2 Gastrointestinal:**

Rule out non-inflammatory causes. If non-inflammatory cause, treat accordingly and continue protocol therapy. Opiates or narcotics may mask symptoms of perforation. Infliximab should not be used in case of perforation or sepsis.

Grade of diarrhea/colitis (NCI CTCAE v4)	Management	Follow-up

Grade 1 Diarrhea of less than 4 stools per day over baseline or asymptomatic colitis
	
 
• Continue nivolumab
 
• Symptomatic treatment such as loperamide
 
	
 
• Close monitoring for worsening symptoms
 
• Educate patient to report worsening immediately
 
• If worsening, treat as grade 2,3 or 4
 

Grade 2
 
 
• Diarrhea of 4-6 stools per day over baseline OR
 
• IV fluids needed < 24 hours due to diarrhea OR
 
• Colitis with abdominal pain or blood in stool
 
	
 
• Hold nivolumab
 
• Symptomatic treatment such as loperamide.
 
	
 
• If improves to grade 1, resume nivolumab and/or IL-2
 
• If symptoms persist for > 7 days             
 
○ 1-2 mg/kg per day of oral prednisone or equivalent
 
○ Consider prophylactic antibiotics for opportunistic infections like PCP
 
○ Resume nivolumab and IL-2 if the event improves to grade 0 or 1 within 12 weeks and corticosteroids have been reduced to the equivalent of ≤ 10mg oral prednisone per day
 
○ When symptoms improve to grade 1, taper steroids over at least one month
 
 
 
• If worsening, treat as grade 3 or 4
 

Grade 3
	
 
• Hold nivolumab
 
	
 
• If improves
 

Grade of diarrhea/colitis (NCI CTCAE v4)	Management	Follow-up

 
• Diarrhea ≥ 7 stools per day over baseline OR
 
• IV fluids needed for ≥ 24 hours due to diarrhea OR
 
• Colitis with severe abdominal pain or medical intervention indicated
 
	
 
• methylprednisolone IV or IV equivalent
 
• Start prophylactic antibiotics for opportunistic infections such as PCP
 
• Consider lower endoscopy
 
	
 
• Continue steroids until symptoms are grade 1, then taper over at least one month
 
• Resume nivolumab and IL-2 if the event improves to grade 0 or 1 within 12 weeks and corticosteroids have been reduced to the equivalent of ≤ 10mg oral prednisone per day
 
• If persists for >3-5 days or recurs after improvement, add infliximab 5mg/kg if no contraindication (Note: infliximab should not be used in cases of perforation or sepsis)
 

Grade 4 Life threatening or perforation	
 
• Discontinue nivolumab
 
• 1-2mg/kg/day methylprednisolone IV or IV equivalent
 
• Start prophylactic antibiotics for opportunistic infections such as PCP
 
• Consider lower endoscopy
 
	
 
• If improves
 
• Continue steroids until symptoms are grade 1, then taper over at least one month
 
• If persists for >3-5 days or recurs after improvement, add infliximab 5mg/kg if no contraindication (Note: infliximab should not be used in cases of perforation or sepsis)
 

